2. **Ohio Autism Clinical Impressions Scale – Improvement (OACIS-I)^{27,28}** is a 7 point, 10 domain scale that requires the clinician to assess how much the patient's ASD has improved or worsened relative to a baseline state at the beginning of the intervention and rated as: “1”, very much improved; “2”, much improved; “3”, minimally improved; “4”, no change; “5”, minimally worse; “6”, much worse; or “7”, very much worse. The 10 domains in which improvement is assessed are the same as those used in the OACIS-S scale. For this study, the proportion of patients who were rated as improved or very much improved on each of 10 domains of OACIS-I were compared between sulforaphane and placebo groups. This scale will be used to gauge the clinician assessment of improvement in autistic symptomatology at all follow up visits as compared to the previous study visits.
 3. **Social Responsiveness Scale (SRS)²⁶**: SRS is a parent- and/or teacher-reported 65 point scale covering 5 treatment subscales focusing on the social communication domain of ASD as observed in natural (non-clinical) settings. Each item on the scale inquires about an observed aspect of reciprocal social behavior that is rated on the questionnaire on a scale from “1” (never true), “2” (sometimes true), “3” (often true), and “4” (almost always true). Its quasi-interval, ordinal design facilitates assessing degrees of change and/or severity of symptoms in response to an intervention. The SRS scale scores is subdivided into 5 subscales (social awareness, social cognition, social communication, social motivation and autistic mannerisms). This scale will be used at all study visits and the scores (as well as change thereof from the baseline visit) will be used as one of the clinical outcome measures assessing social interaction skills in the study.

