At this visit, the study participant/s will already have been randomly assigned to either the sulforaphane or placebo group in the ratio of 1:1 by the study statistician. As mentioned above, after the safety labs come back normal, we will mail the study participants (or ask their parents to pick up) an 8 week supply of study medication (sulforaphane or placebo) that will last until the 7 week visit, plus a one week buffer. We will provide detailed instructions to subjects/parents/guardians on how to take the medication and include these instructions along with the medication package, and they will be made aware (and given written instructions) on how to recognize any side effects associated with the medication. They will be asked to call the study staff in case they have any questions or concerns.

2. **7 week visit (double blind Phase 1):** Enrolled subjects will then be asked to come for their 7 week (follow-up) study visit, where OACIS-I, SRS, ABC and Vineland Adaptive Behavior Scale will be administered. A complete physical examination will be performed and vital signs obtained. This visit will take ~ 1.5 hours to complete. They will be asked about any serious side effects they might have experienced. Also, clinical laboratory tests (CBC and platelets, complete metabolic profile (including liver function tests, renal function tests, thyroid function tests) and research laboratory tests blood - (Nrf2, heat shock proteins, measures of oxidative stress and mTOR) and urine (isoprostanes) will be obtained. Maximum amount of blood drawn at any stage during this study will not exceed 2 ml/kg body weight; we will also not exceed the minimal risk limitation of 3 ml/kg in an 8 week period.

At this visit, we will give the study participants a further 7 week supply of study medication (sulforaphane or placebo) that will last until the next visit (15 week visit). Study participants will be asked to finish the medication from the previous lot before starting the latter batch. They will be asked to continue to take the study medication unless instructed otherwise. We will provide detailed instructions for subjects/parents/guardians on how to take the study medication along with the medication package, and they will be made aware (and given written instructions) on how to recognize any side effects associated with the study medication. They will be asked to call the study staff in case they have any questions or concerns.

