Visit	Informed consent, eligibility criteria (ADOS, Leiter-3)	Adverse event reporting	Medical history, vitals, physical exam	Autism symptom severity (OACIS-S, OACIS-I, ABC, SRS, Vineland Adaptive Behavior Scale)	Blood draw (LFTs, RFTs, TSH, CBC, HSP, mTor, Nerf), urine sample for isoprostanes	Study drug dispensing	Visit duration
Double blind phase (50% participants receive sulforaphane and 50% receive placebo)							
Screening/ baseline visit	X		X	X	X	8 weeks	~ 2.5 hours
3 week phone survey		X					~ 15 minutes

7 week visit		X	X	X	X	7 weeks	~ 1.5 hours
15 week visit		X	X	X	X	8 weeks	~ 1.5 hours
Open label phase (all participants receive sulforaphane)							
18 week phone survey		X					~ 15 minutes
22 week visit		X	X	X	X	7 weeks	~ 1.5 hours
30 week visit		X	X	X	X		~ 1.5 hours
36 week visit		X	X	X	X		~ 45 minutes

11) Data and Specimen Banking*

We plan to store leftover blood and urine samples in -80 C freezer in the Dept. of Pediatrics at UMass and the Cullman Chemoprotection Laboratory at Johns Hopkins for a period of 3 years after completion of the study. They will be accessed by the P.I. or study staff. The samples will continue to be de-identified and labeled with unique study I.D. numbers. The link between the study ID and identifiable information will only be accessible by the UMass personnel. At the end of 3 years the samples will be forever anonymized, and the link between study ID and identifiable information will be destroyed. We will make application to the IRB for any further studies to be conducted, by ourselves or others, using these specimens.

12) Data Management*

Statistical Analysis: The OACIS-I, SRS and ABC data will be analyzed in a mixed model ANOVA with fixed effects for visit, treatment group, and their interaction and random participant-specific intercepts. The effect of sulforaphane on mean change in OACIS-I, SRS and ABC total scores from baseline will be estimated using linear contrasts. Estimates will be unbiased if any loss to follow-up is missing at random, conditional on the observed data and our model assumptions. Significantly greater improvement from baseline in mean scores among participants randomized to sulforaphane based on a two-tailed test at $\alpha = 0.05$ will be taken as support of our primary hypothesis.

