A secondary analysis assessing proportion of participants in both groups who have responded to the study drug will be performed by Fisher's Exact test. This analysis will be done by categorizing the OACIS-I, SRS and ABC data. Participants will be considered as responders to study drug if they experience either of the following: they are much/very much improved (a score of 2 or less) on any subdomain of OACIS-I scale, their total ABC scores at 15 weeks decrease by at least 25% from baseline score, and their total SRS scores at 15 weeks decrease by at least 25% from their baseline score.

Biomarkers (testing mechanism of action of SFN) will be tested both as outcome variables in mixed model analyses and as predictors of differences in behavioral symptoms using the models described above for behavioral symptoms. Markers that both respond to sulforaphane treatment and predict differences in behavioral symptoms will be interpreted as possible mediators of any benefit from sulforaphane treatment. Safety of sulforaphane treatment will be assessed based on absolute rates of liver, thyroid and renal toxicity among participants treated with sulforaphane and based on comparison of the proportion of participants with such toxicities between the two treatment groups.

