Power Calculations: We plan to enroll a total of 50 participants in the study, randomized 1:1 to sulforaphane and placebo. With OACIS-I, ABC, and SRS assessments at 0, 7 and 15 weeks our proposed design will have at least 80% power to detect significance in the following outcome measures if the following sample sizes are considered: **OACIS-I average Score:** With a total of 40 patients (20 on placebo and 20 on sulforaphane) entering this two-treatment parallel-design study, the probability is 80 percent that the study will detect a treatment difference at a two-sided 0.05 significance level, if the true difference of average OACIS-I score at 15 weeks between two treatments is 4 units. This is based on the assumption that the standard deviation of the average OACIS-I score is 4.9. **OACIS-I response rate on aberrant behaviors:** With a total of 44 patients (22 on placebo and 22 on sulforaphane) entering this two-treatment parallel-design study, there will be an 88% chance of detecting a significant difference at a two sided 0.05 significance level. This assumes that the response rate at 15 weeks of placebo is 9% and the response rate of sulforaphane is 54% on aberrant behavior subscale of OACIS-I. **OACIS-I response rate on social communication:** With a total of 44 patients (22 on placebo and 22 on sulforaphane) entering this two-treatment parallel-design study, there will be 82% chance of detecting a significant difference at a two sided 0.05 significance level. This assumes that the response rate of placebo is 7% and the response rate at 15 weeks of sulforaphane is 46% on the social communication subscale of OACIS-I. **Change in total ABC score from baseline:** With a total of 44 patients (22 on placebo and 22 on sulforaphane) entering this two-treatment parallel-design study, the probability is 81 percent that the study will detect a treatment difference at a two-sided 0.05 significance level, if the true difference of change in baseline of total ABC score at 15 weeks between the two treatments is 19.4 units. This is based on the assumption that the standard deviation of the change in ABC score is 22.1. **Change in total SRS score from baseline:** With a total of 48 patients (22 on placebo and 22 on sulforaphane) entering this two-treatment parallel-design study, the probability is 81 percent that the study will detect a treatment difference at a two-sided 0.05 significance level, if the true difference of change from baseline of total SRS score at 15 weeks between two treatments is 18.4 units. This is based on the assumption that the standard deviation of the change in SRS score is 22.0. Thus our proposed sample size of 50 participants, randomized 1:1 to sulforaphane and placebo will have more than enough power to detect significantly changes in majority of the outcomes listed above. The study will have 80% power to detect one or more toxicities expected to occur in at least 5.3% of sulforaphane-treated participants. The study is not powered to compare rates of safety outcome between sulforaphane and placebo treatment groups for a relevant non-inferiority threshold.

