Participants will be compensated for their participation in the study. We will provide them with a gift card worth \$15 for each completed study visit. We will also provide them with parking vouchers when families park their vehicle in the UMass Medical Center parking lot. Children will be given a small soft toy to keep.

Flyers describing the nature of sulforaphane and how it might help ASD will be used for study advertisement. These advertisements will make it clear that it is a research study and not a "free treatment program" for ASD, in order to remove any coercive or undue inducements for study participation. These flyers will be distributed to various autism advocacy centers for display purposes, and may also be distributed by email based listservs.

The recruitment process is similar for both the pilot study as well as the main clinical trial.

Screening Procedures:

Prior to coming for the formal screening visit, all subjects will undergo a pre-screen assessment to determine if basic eligibility criteria are met and the study procedures will be explained in detail. Qualified study staff will ask questions related to the above described inclusion/exclusion criteria. The pre-screen may be completed by telephone or direct interview. If a participant is found to be ineligible for the study, prescreening form will be destroyed.

At the screening visit, *after* the consent has been signed by parents/guardians and assent signed (if applicable), a complete, baseline medical history, physical and neurological exam will be performed. During that visit, ADOS-G, SRS, OACIS-Severity scale and ABC-W scales will be performed to confirm eligibility and to quantify disease severity. Also, following laboratory blood tests (complete blood count, comprehensive metabolic profile: liver function tests, renal function tests, thyroid function test (TSH)) will be performed. Maximum amount of blood drawn at any stage during this study will not exceed 2 ml/kg body weight; we will also not exceed the minimal risk limitation of 3 ml/kg in an 8 week period.

25) Local Number of Subjects

We will enroll 50 participants in the study. We anticipate that 400 to 500 families will be screened in order to attract 50 participants.

26) Confidentiality

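### For the secondary outcomes ABC and SRS, adjust for the baseline already collected and replace the random-intercept covariance; settle what OACIS-I is rated against before modelling the primary outcome

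*Combined protocol and SAP*

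**What the plan says.** Section 12, Statistical Analysis, specifies a "mixed model ANOVA with fixed effects for visit, treatment group, and their interaction and random participant-specific intercepts" for OACIS-I, SRS and ABC. It adds that "The effect of sulforaphane on mean change in OACIS-I, SRS and ABC total scores from baseline will be estimated using linear contrasts". It names no week for the contrast, no baseline covariate and no other covariance structure.

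Week 15 appears nearby. The responder rule in the same section uses it ("their total ABC scores at 15 weeks decrease by at least 25% from baseline score"), and Power Calculations opens with "With OACIS-I, ABC, and SRS assessments at 0, 7 and 15 weeks our proposed design will have at least 80% power" and then states its effects at 15 weeks. The scales are also completed at weeks 22, 30 and 36, when all children are on open-label drug or off drug. The model paragraph does not say that those visits are left out.

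The baseline values exist. Under section 24, Screening Procedures, "ADOS-G, SRS, OACIS-Severity scale and ABC-W scales will be performed to confirm eligibility and to quantify disease severity".

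Section 9 describes OACIS-I in two ways. It is a rating of how far the child has "improved or worsened relative to a baseline state at the beginning of the intervention", and it will also gauge "improvement in autistic symptomatology at all follow up visits as compared to the previous study visits". The visit narrative in section 10 gives OACIS-S at screening and first gives OACIS-I at the "7 week (follow-up) study visit, where OACIS-I, SRS, ABC and Vineland Adaptive Behavior Scale will be administered". Power Calculations nevertheless lists OACIS-I at week 0.

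**The concern.** There are two separate issues for ABC and SRS, both secondary outcomes.

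- **Precision.** Measuring change from baseline is not the same as adjusting for baseline. The change score subtracts the whole baseline value whatever its correlation with week 15. Regression on baseline subtracts only the part that predicts, so it usually has a smaller variance.
- **Standard error.** A random intercept gives every pair of visits the same difference variance. If week 0 and week 15 are less alike than neighbouring visits, the week-15 standard error is too small and the test rejects too often. If they are more alike, the test is conservative.

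At stake are some power from data already in hand and an error rate that should not depend on unknown correlations.

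For the primary OACIS-I the question is more basic. If the week-15 rating is made against the previous visit, it measures change since week 7, and a week-15 contrast is not the effect of 15 weeks of treatment.

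**Working it through.** **Inputs from Power Calculations.** ABC: difference 19.4, SD of change 22.1. SRS: difference 18.4, SD of change 22.0. Two-sided 0.05; 50 children, 25 per arm. The correlation r between week 0 and week 15 is not given, so it is assumed.

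**Plan's own figures (two-sample t, noncentral).** ABC at 22 per arm: 81.2%, matching the stated 81%. SRS at 24 per arm (total 48): 81.0%, matching the stated 81%. SRS at the printed 22 + 22: 77.3%, which does not match.

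**Power of the planned model at 25 per arm.** With complete data and equal correlations, the noncentrality is difference / (SD × √(2/25)): SRS 18.4/(22.0 × 0.2828) = 2.957; ABC 19.4/(22.1 × 0.2828) = 3.104. The model pools residual degrees of freedom over weeks 0, 7 and 15: 2 × (50 − 2) = 96. Power is 83.3% for SRS and 86.7% for ABC. A plain t-test on change, with 48 degrees of freedom, gives 82.6% and 86.0%.

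**Power with baseline adjustment.** With equal SDs σ, the change score has variance 2σ²(1 − r) and the adjusted outcome σ²(1 − r²). The ratio is (1 + r)/2. At r = 0.5 the SRS SD falls from 22.0 to 22.0 × √0.75 = 19.05; at r = 0.8 to 22.0 × √0.90 = 20.87. The simulated power below (100,000 trials) includes the cost of estimating the slope.

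| assumed r | 0.5 | 0.6 | 0.7 | 0.8 | 0.9 |
|---|---|---|---|---|---|
| variance ratio | 0.75 | 0.80 | 0.85 | 0.90 | 0.95 |
| SRS power (planned 83.3%) | 91.1% | 89.3% | 87.6% | 85.6% | 83.3% |
| ABC power (planned 86.7%) | 93.5% | 92.0% | 90.5% | 88.6% | 86.9% |

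**Unequal SDs.** With k = week-15 SD / baseline SD, the ratio is k²(1 − r²)/(1 + k² − 2rk). For r = 0.5-0.8 it is 0.57-0.64 at k = 0.8 and 0.87-1.00 at k = 1.2, so at k = 1.2 the gain is small or nil.

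**Type I error of the planned test, weeks 0, 7 and 15.** At unit variance, each pair's difference variance is 2(1 − r). The random-intercept model uses their mean. Let q = √(mean / true week 0-15 variance); the error is then about 2[1 − Φ(1.96q)]. Example with r(0-7)/r(7-15)/r(0-15) = 0.7/0.7/0.6: the pair variances are 0.6, 0.6 and 0.8, with mean 0.667; q = √(0.667/0.8) = 0.913; error 7.4%. Simulation used 25 per arm and 40,000 null trials per pattern.

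| r(0-7)/r(7-15)/r(0-15) | q | simulated, planned test | simulated, week-15 ANCOVA |
|---|---|---|---|
| 0.7/0.7/0.7 | 1.00 | 5.1% | 5.1% |
| 0.65/0.65/0.6 | 0.96 | 5.8% | 4.9% |
| 0.7/0.7/0.6 | 0.91 | 7.4% | 5.0% |
| 0.8/0.8/0.7 | 0.88 | 8.2% | 4.9% |
| 0.8/0.8/0.64 (autoregressive) | 0.84 | 10.0% | 4.9% |
| 0.6/0.6/0.7 | 1.11 | 3.0% | 5.2% |

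**A baseline covariate alone is not enough.** With the random intercept kept on weeks 7 and 15, simulated error was 5.1-8.2% at equal SDs, and 7.2% when the week-15 SD was 1.2 times the week-7 SD. The covariance has to be freed as well.

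**OACIS-I.** With weeks 7 and 15 and equal SDs, the planned test's simulated error was 5.1-5.2%, so no fault is shown there. Its power cannot usefully be recalculated: an average of items scored 1-7 has a range of 6, hence an SD of at most about 6/2 = 3, while Power Calculations assumes 4.9.

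**The case against.** The other side has a fair case. The change-score contrast is a valid estimator, ABC and SRS are secondary, and no documented figure shows that the planned test errs. The right comparator is the planned model with its pooled degrees of freedom, which makes the gain at r = 0.8 only about 2 points (SRS 83.3% to 85.6%). All of that stands, and the sizes above reflect it. It does not remove the point: the planned error rate depends on correlations nobody has stated, and the alternative's does not.

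The proposed model also has a cost. Taking only weeks 7 and 15 as responses drops children with no post-baseline visit, whereas the planned model keeps their week-0 value. The simulations assume complete data and do not address this.

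A reader might infer more than the documents support:

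- **That the type I error is inflated.** It may be, but some patterns make the test conservative. Unknown is the supportable word.
- **That adjustment carries SRS power across 80%.** This needs 22 per arm. The printed total of 48 conflicts with 22 + 22, the stated 81% reproduces at 24 per arm, and at the planned 25 unadjusted power already exceeds 80%.
- **That all six visits enter the efficacy model.** Error rates under that reading reach 13.3% for some assumed correlations, but the responder rule and Power Calculations point to weeks 0, 7 and 15. It is a reason to state the restriction, not evidence of a fault.
- **That the primary analysis gains a known amount of power.** No figure should be drawn from the SD of 4.9.

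**Conclusion.** The point holds for ABC and SRS as an improvement that should be made, with medium confidence. The planned contrast is unbiased with complete data but usually less precise than a baseline-adjusted one. At 25 per arm with equal SDs, adjustment adds roughly 8 to 2 points of power for SRS and 7 to 2 for ABC as the assumed correlation goes from 0.5 to 0.8. The gain is close to nil at 0.9, and small or nil if the week-15 SD is about 1.2 times baseline. The planned test's type I error lies between about 3% and 10% over the patterns tried. These sizes rest on assumed correlations, normal data and no missing visits.

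For the primary OACIS-I no error is shown at equal variances, and any gain is uncertain. What does hold is the contradiction in section 9 over the reference point, together with the unexplained week-0 entry in Power Calculations. Until these are reconciled, the week-15 contrast has no single meaning.

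**What to change.** 1. **ABC and SRS.** State that the efficacy model uses weeks 7 and 15 as responses, with treatment, visit, treatment-by-visit, baseline score and baseline-by-visit, unstructured within-child covariance and Kenward-Roger degrees of freedom. Name the week-15 treatment contrast as the test.
2. **Later visits.** State that weeks 22, 30 and 36 are analysed separately.
3. **OACIS-I.** Reconcile section 9 so that the rating has one stated reference and the week-15 score measures change from baseline. Remove or explain the week-0 OACIS-I entry and enter no week-0 value in the model. Then use the same model with baseline OACIS-S as the covariate.

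The cost is SAP wording and a few lines of code, with no new data or visits. The downsides are a few more parameters (three covariance terms for two visits) and the loss of children with no post-baseline visit. A constrained model that keeps week 0 as a response, with equal baseline means in the two arms, would retain those children.

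### The primary OACIS-I contrast is written as change from baseline, but OACIS-I has no defined week-0 value; state it as the week-15 difference between arms

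*Combined protocol and SAP*

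**What the plan says.** Section 9 makes the OACIS-I average score the primary endpoint and lists ABC and SRS as changes in total score. It describes OACIS-I as a 10-domain scale scored 1 to 7, with 4 meaning no change, on which the clinician judges whether the child has "improved or worsened relative to a baseline state at the beginning of the intervention". The same description ends by calling it an "assessment of improvement in autistic symptomatology at all follow up visits as compared to the previous study visits".

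Section 12 (Statistical Analysis) analyses OACIS-I, SRS and ABC together in a mixed model with "fixed effects for visit, treatment group, and their interaction and random participant-specific intercepts". It then states: "The effect of sulforaphane on mean change in OACIS-I, SRS and ABC total scores from baseline will be estimated using linear contrasts". Greater improvement from baseline, two-tailed at 0.05, counts as support for the primary hypothesis.

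The documents disagree on when OACIS-I is first rated:

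- The screening visit in section 10 and the Screening Procedures in section 24 list OACIS-S only. Section 10 first lists OACIS-I at week 7. The timeline in section 8 has the same pattern, under the names CGI-S and CGI-I.
- The visit table in section 10 ticks one combined column, "Autism symptom severity (OACIS-S, OACIS-I, ABC, SRS, Vineland Adaptive Behavior Scale", at baseline as well as later. Section 12 (Power Calculations) says "With OACIS-I, ABC, and SRS assessments at 0, 7 and 15 weeks our proposed design will have at least 80% power".

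The power text sizes OACIS-I as a week-15 comparison, "if the true difference of average OACIS-I score at 15 weeks between two treatments is 4 units", assuming "the standard deviation of the average OACIS-I score is 4.9". It sizes ABC and SRS as changes from baseline.

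**The concern.** ABC and SRS are scored at baseline, so a change-from-baseline contrast is well defined for them. OACIS-I already measures change. Subtracting a baseline from it needs a week-0 OACIS-I score, and no section says what that score is. OACIS-S cannot stand in, because it rates severity on a different scale.

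The analyst must therefore decide what, if anything, goes in the week-0 row. One choice is to leave it out. The other natural choice is to enter 4 in every domain for every child, since nothing can have changed at the start. Both give the same point estimate, but they give different standard errors in the stated model and so different p-values for the primary test. That decision should not be left until data are in hand.

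Two neighbouring definitions of the same score are also unsettled: the state against which the rater compares, and whether the score is a mean or a sum of the ten domains.

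**Working it through.** **1. The plan's own power figure.** Inputs from section 12: difference 4, SD 4.9, two-sided 0.05, 20 per arm, stated power 80%. The noncentrality is 4 / (4.9 × √(2/n)).

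| Per arm | Noncentrality | df | Critical t | Power |
|---|---|---|---|---|
| 20 | 2.58 | 38 | 2.02 | 71% |
| 25 | 2.89 | 48 | 2.01 | 81% |

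The stated 80% is not reproduced at 20 per arm. The planned 50 children give it, if all have week-15 data.

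**2. Point estimate with a constant week-0 row.** The contrast is (week 15 − constant) on sulforaphane minus (week 15 − constant) on placebo. The constant cancels, leaving the week-15 arm difference.

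**3. Standard error with that row.** Let weeks 7 and 15 each have variance σ² and correlation ρ. Week 0 has variance 0 and covariance 0 with the others.

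- The random-intercept model assumes one residual variance. Its expected value is the average variance minus the average covariance over the three visits: 2σ²/3 − ρσ²/3 = σ²(2 − ρ)/3.
- Model variance of the contrast: 4/n × σ²(2 − ρ)/3.
- True variance of the week-15 arm difference: 2σ²/n.
- Ratio, model to true: 2(2 − ρ)/3. This equals 1 only at ρ = 0.5.

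**4. Type I error.** The documents give no correlation, so a range is assumed. Simulation used 25 per arm, complete data, equal SDs and no true effect.

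| Assumed ρ | Variance ratio | Model SE / true SE | Type I error, constant row | Week-15 t-test |
|---|---|---|---|---|
| 0.3 | 1.13 | 1.06 | 3.7% | about 5% |
| 0.5 | 1.00 | 1.00 | about 5% | about 5% |
| 0.7 | 0.87 | 0.93 | 6.7% | about 5% |
| 0.8 | 0.80 | 0.89 | 7.9% | about 5% |

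The random-intercept model fitted to weeks 7 and 15 only, under the same assumptions, also holds about 5% (4.9% to 5.1%).

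**5. Scale of the score.** An average of ratings between 1 and 7 has its largest SD when half the values lie at each end: (7 − 1)/2 = 3. An SD of 4.9 is out of reach. A 4-unit arm difference would need a placebo mean of at least 1 + 4 = 5, on the worse side of no change, even if every treated child scored 1. On a 10-domain sum the same inputs are 4/10 = 0.4 and 4.9/10 = 0.49 per domain, which is possible.

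**The case against.** The best defence is that the plan largely answers the question elsewhere. Section 9 names OACIS-I as a score and ABC and SRS as changes, and the power text keeps that split. Read with the scale's definition, the shared sentence in section 12 most naturally means the week-15 arm difference, and no passage tells anyone to enter a constant row. The effect is also modest, has no fixed direction, and vanishes if week 0 is left out. All of this stands, and it limits the weight of the point. It does not remove it: the analysis text still states another contrast, the power text and the visit table still place OACIS-I at week 0, and neither says what is recorded there.

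A reader might infer more than the documents support:

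- *That the primary test has an inflated error rate.* Inflation needs both a constant row, which the plan does not prescribe, and a correlation above 0.5, which it does not give.
- *That the parents' recalled OACIS impressions of fever and illness, taken at screening (section 10), are the week-0 score.* They are part of the history, rate a different change, and are never called a baseline.
- *That each rating covers only the interval since the last visit, with a loss of power.* Section 9 first sets the reference at the start of the intervention, and its later mention of previous visits is plural and may include baseline. The two statements need reconciling; no power loss can be computed from them.
- *That section 10's five OACIS visits in a six-visit study prove there is no baseline OACIS-I.* That sentence names OACIS without the form, and a miscount is equally plausible.

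**Conclusion.** The point holds as a defect of specification in the primary analysis that should be fixed. As written, the OACIS-I contrast needs a week-0 value the plan does not define. With no week-0 value the change contrast cannot be formed as stated. With the constant implied by the scale, its standard error is right only when the week 7–15 correlation is near 0.5; over assumed correlations of 0.3 to 0.8, a nominal 5% test runs at about 3.7% to 7.9%. Those figures rest on 25 per arm, complete data and equal SDs at the two visits. The estimate itself is not biased by the constant row.

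Two linked findings need no assumed correlation. SD 4.9 is incompatible with an average of 1–7 ratings, whose maximum SD is about 3, and the 4-unit difference is implausible on that scale. The stated 80% power at 20 per arm computes to 71%, against 81% at 25 per arm with complete data.

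**What to change.** - In section 12, state the primary OACIS-I contrast as the between-arm difference at week 15, estimated from post-baseline visits with no week-0 row. Keep change from baseline for ABC and SRS.
- In the power text, remove week 0 for OACIS-I. The OACIS-I calculation there does not use it.
- Split the visit-table column so that OACIS-S is ticked at baseline and OACIS-I from week 7, and align the other mentions of OACIS timing in section 10.
- In section 9, reconcile the two reference states into one and give raters the matching instruction.
- State whether the score is the mean or the sum of the ten domains, restate the difference and SD on that scale, and give the power with its sample size.

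An unstructured covariance for the repeated visits is a separate, optional modelling choice; this correction does not depend on it.

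The cost is protocol and analysis-plan wording, one rater instruction and a few lines of code. No new data, visits or participants are needed: the planned 50 children give 81% power on the plan's own inputs if all provide week-15 data.
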